2.2 Definition of baseline date

Baseline is referred to as Visit 1 (Day 0) of the study. It is defined as:

- the date of the first administration of study treatment, for treated subjects
- the date of randomization, for subjects who are randomized but not exposed to any study treatment

2.3 Baseline and post-baseline definitions

The baseline value for efficacy and safety variables is the last available, non-missing, scheduled or unscheduled value collected prior to exposure to study treatment. If a subject is

randomized but not treated then the baseline value for a variable is the last available non-missing value collected prior to randomization.

Some baseline assessments may be recorded on the day of the baseline visit (Visit 1). Since the time of the first study treatment at this visit is not recorded in the electronic case report form (eCRF), it is not possible to determine which baseline assessments at the baseline visit (Visit 1) were undertaken before and which after the first study treatment. Hence, only the assessments which, according to the protocol, should have been conducted pre-dose will be assumed to have been done before the first study treatment when deriving baseline values recorded on the day of the baseline visit (Visit 1).

All data collected after Visit 1 (Day 0) are defined as post-baseline.

2.4 Visit windowing

2.4.1 Early exit visits

Visit windowing will be performed for the early exit visit. The study day for this visit will be derived based on the following definition:

$$\text{Study day} = (\text{Date of visit}) - (\text{Date of baseline visit}) + 1$$

The study day for the early exit visit will be allocated to the nearest planned visit (see Table 2-1).

Table 2-1 Visit windows

Visit timepoint	Scheduled visit study day	Visit window (study days)
Screening Visit	< -7	-14 to -7
Visit 1 (Day 0/ Baseline)	0	0
Visit 2 (Day 15 ± 3)	15	2 to 24
Visit 3 (Day 35/ End of Treatment ± 3)	35	>=25

If data for the nearest planned visit already exist then the early exit visit will be assigned to the next visit.

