2 OVERVIEW OF STUDY PLAN

Table 2-1 Schedule of Assessments

Procedure/ Assessment ¹	Screening	Visit 1 (Baseline)	Visit 2	Visit 3 (Exit)	Early Exit	Unscheduled
	Day -14 to -7	Day 0	Day 15 ± 3 days	Day 35 ± 3 days		
Informed consent	X					
Demographics	X					
Medical history	X					
Changes to medical conditions		X	X	X	X	X
Concomitant medications	X					
Changes to concomitant medications		X	X	X	X	X
Urine pregnancy test ²	X			X	X	
Inclusion/exclusion criteria	X					
Undilated fundus examination	X					
Unanesthetized Schirmer I test	X					
Intraocular pressure	X					
Start run-in phase Saline	X ³					
Dispense run-in phase Saline	X					
Stop run-in phase Saline		X				
Collect run-phase Saline empty and unused bottles		X				
Randomization		X				
Dispense treatment phase study products (SYSTANE BALANCE or REFRESH OPTIVE Advanced)		X	X			X ⁴
Collect treatment phase study products (SYSTANE BALANCE or REFRESH OPTIVE Advanced)			X	X	X	X ⁴
Ocular Discomfort assessment		X	X	X	X ²	
BCVA	X	X	X	X	X	X
Slit-lamp examination	X	X	X	X	X	X
Tear film break-up time	X	X	X	X	X ²	
Lipid layer thickness		X	X	X	X ²	
Adverse events (both volunteered and elicited)	X	X	X	X	X	X
Electronic data capture	X	X	X	X	X	X
Complete exit form				X	X	

- For eligible study subjects, all study assessments during each visit must be conducted at the same time of day within ± 1 hour of the start time of Visit 1 (Baseline).
- For women who are of child bearing potential.
- Preservative-free saline will be administered for 7 to 14 days prior to baseline i.e. from Day -14/Day -7 to Day -1.
- If necessary.
- These assessments should only be done if study subject exits the study early prior to Day 35 but has been on masked treatment for at least 14 days.

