10.2 Visits and Examinations

Subjects should come in for all regularly scheduled visits (even if a visit is “out of window”). Visit 3 (Day 35) is critical for evaluating the subject’s response to therapy after completing the designated dosing period.

The schedule of study procedures/ assessments is presented in Table 2–1. For details of the procedures used and order of assessments in this protocol, refer to the manual of procedures (MOP). For eligible study subjects, all study assessments during each visit must be conducted at the same time of day within ± 1 hour of the start time of Visit 1 (Baseline). Adverse events (AEs) will be collected from the time of informed consent, until the subject exits the study. All AEs that are observed or reported should be recorded on an AE form as per Section 12.2 and reported to the IRB/IEC, as required.

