11.5 Handling of Missing Data

The mixed-effects repeated measures (MMRM) model approach will be used to analyze the continuous variables. The MMRM model is suitable for longitudinal data with missing values

under the missing at random (MAR) assumption. It is a likelihood-based analysis that can provide valid inference without the need for explicit modeling or imputation of missing data.

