2.4.2 Unscheduled visits

All data collected at unscheduled visits will be listed.

Adverse event (AE) and exposure to study treatment data collected at unscheduled visits will be used.

3 Analysis Sets

The **Screened Set (SCR)** will consist of all subjects who signed the informed consent form (ICF).

The **Randomized Set (RS)** will consist of all subjects who were randomized to one of the study treatment arms.

The **Full Analysis Set (FAS)** is used to describe the analysis set which is as complete as possible and as close as possible to the intent-to-treat (ITT) principle of including all randomized subjects. The FAS will include all randomized subjects who have at least 1 post-baseline primary endpoint (TFBUT) assessment.

The **Per Protocol Set (PPS)** will consist of FAS subjects who satisfy all inclusion/ exclusion criteria and who have no major PDs, which will be specified in the Deviations and Evaluability Plan (DEP).

The **Safety Analysis Set** will include all subjects exposed to post-randomization study product.

Evaluability for all subjects will be determined prior to breaking the code for masked study treatment assignment.

The primary and secondary efficacy analyses will be performed on both the FAS and PPS with the PPS providing the primary inference for the non-inferiority hypothesis and the FAS providing the primary inference for the superiority hypotheses.

Supportive analyses of the primary hypothesis will be conducted using the FAS. Similarly, supportive analyses of the secondary hypotheses will be conducted using the PPS.

The number of subjects excluded from the FAS and PPS and a listing of excluded subjects with reason for exclusion will be presented. Any inconsistencies in key study results between the FAS and PPS will be examined and discussed in the CSR.

All efficacy analyses will be according to randomized assignment (regardless of the study treatment they received).

Safety analyses will be conducted using the Safety Analysis Set on a treatment-emergent basis. The main safety analyses will focus on the investigational products (SYSTANE BALANCE, REFRESH OPTIVE Advanced/ OPTIVE PLUS [UK]). For treatment-emergent safety analyses, subjects will be categorized under the actual study treatment received.

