Evidence of efficacy (non-inferiority) will be deemed established if the lower limit of the 95% CI (equivalent to the 1-sided 97.5% CI) for the adjusted estimate of the difference (SYSTANE BALANCE - REFRESH OPTIVE Advanced/ OPTIVE PLUS [UK]) is above - 1.0 second (non-inferiority margin). The non-inferiority margin was chosen as 1.0 second on the basis that an increase of at least 25% in the baseline TFBUT of a subject with lipid-deficient dry eye would be considered clinically meaningful since the subject would blink less often.

The analysis set for the primary efficacy assessment will be the PPS. As a sensitivity analysis, the analysis will be repeated for the FAS using the same model.

Observed values and change from baseline values for the analysis eye for the PPS and FAS will also be presented descriptively (N, mean, median, SD, standard error [SE], minimum, and maximum) at each study visit for each study treatment. A plot of mean change in TFBUT by study visit and study treatment with error bars representing +/- 1 SE will be presented using the analysis eye. The x-axis will be study visit and the y-axis will be the change in TFBUT from baseline.

Observed values from all visits for the RS will also be listed along with the following variables: treatment, investigator, subject, age, sex, race, ethnicity, visit, eye, baseline value, and value at the visit.

The analysis of the secondary efficacy parameters will also be based on a MMRM model. The mixed model will include terms for the respective baseline parameter value (continuous), study treatment (SYSTANE BALANCE, REFRESH OPTIVE Advanced/ OPTIVE PLUS [UK]), visit (Day 15 [Visit 2], Day 35 [Visit 3]), and study treatment-by-visit interaction. The same procedure as outlined for the primary efficacy analysis in selecting the best fitting covariance structure will be applied. Estimates of the difference in mean change from baseline between SYSTANE BALANCE and REFRESH OPTIVE Advanced/ OPTIVE PLUS (UK) and the associated 95% CIs in the analysis eye will be presented.

Each secondary endpoint will be evaluated for superiority of SYSTANE BALANCE over REFRESH OPTIVE Advanced/ OPTIVE PLUS (UK).

The analysis set for the secondary efficacy assessments will be the FAS. As a sensitivity analysis, the analysis will be repeated for the PPS using the same model.

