11.1 Change to protocol specified analyses

LLT will only be listed in this study. In the protocol, it was originally planned to analyze LLT as part of the secondary [REDACTED] endpoints. However the device used to measure LLT was unable to provide a credible LLT value if the LLT value was greater than 100 nm.

Therefore as this impacted at least 25% of the LLT values, it was agreed by the clinical trial team with input from upper management to only list the LLT data.

At the time of the second amended Statistical Analysis Plan, subject follow-up is complete and all subjects have exited the study. The study database is not yet locked and masked treatment code has not been broken. Due to the fact that subject follow-up is complete and the current change to analysis strategy is an operational matter with no impact on study design or subject safety, the decision was taken only to amend the Statistical Analysis Plan and not undertake a corresponding amendment to the protocol.

12 Appendix

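### The early-exit rule can file a TFBUT taken 12 to 21 days early as the Day 35 value, and the study-day formula does not match its own window table

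*SAP*

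**What the plan says.** SAP section 2.4.1 computes study day for an early-exit visit as visit date minus baseline date plus one, and allocates it to the nearest planned visit using SAP Table 2-1. That table has Visit 1 at day 0, Visit 2 scheduled at day 15 (window 2 to 24) and Visit 3 scheduled at day 35 (window 25 and above). It continues: "If data for the nearest planned visit already exist then the early exit visit will be assigned to the next visit". No minimum day is given for a value to count as Visit 3.

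Protocol Table 2-1 schedules TFBUT and the ocular discomfort assessment at early exit. A footnote limits this to a subject who "exits the study early prior to Day 35 but has been on masked treatment for at least 14 days". Protocol sections 10.2.2.1 and 10.2.2.2 place Visits 2 and 3 at 15 ± 3 and 35 ± 3 days after Visit 1. Protocol section 10.2 treats Visit 3 as critical because it measures the "response to therapy after completing the designated dosing period".

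For missing data, Protocol section 11.5 relies on the MMRM under MAR, "without the need for explicit modeling or imputation of missing data". SAP Table 5-1 lists a likelihood-based approach for every primary and secondary analysis. SAP section 3 takes the noninferiority inference from the PPS and the superiority inference from the FAS. For the primary endpoint, SAP section 5.3 adds: "As a sensitivity analysis, the analysis will be repeated for the FAS using the same model".

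**The concern.** A subject who leaves shortly after Visit 2 has not had the full dosing period, yet the exit reading enters the Day 35 cell as if it had been observed there. With Visit 2 on Day 15 and exit on Day 16, a TFBUT taken one day after the Visit 2 reading becomes the Day 35 result. In effect this carries an early observation forward without calling it imputation. It also pre-empts the stated method, under which Day 35 would be missing and the model would use the Visit 2 value.

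The Day 35 cell supplies the primary estimate and both remaining secondary estimates, since the Global Ocular Discomfort score follows the same windowing. The planned FAS and PPS runs share one model and one windowing rule, so comparing them does not isolate the effect.

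The mismatch between formula and table is a smaller matter of day counting.

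**Working it through.** **Notation.** Let *d* be days elapsed since Visit 1, so study day *s* = *d* + 1 under the SAP formula.

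**Inputs.** Windows and rule: SAP 2.4.1. Early-exit TFBUT from *d* = 14: Protocol Table 2-1 footnote. Visit 2 at *d* = 12 to 18 and Visit 3 at *d* = 32 to 38: Protocol 10.2.2.1 and 10.2.2.2. SD 2.5, margin 1.0 s and 200 evaluable subjects (100 per arm): SAP section 9.

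**1. Where each exit value goes**

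| Exit day *d* | Study day *s* | Visit 2 data present | Visit 2 data absent |
|---|---|---|---|
| 14–23 | 15–24 | Visit 3, by the next-visit sentence | Visit 2 |
| 24–34 | 25–35 | Visit 3, by the window | Visit 3, by the window |

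**2. Mistiming of the values that roll forward.** 35 − 23 = 12 days to 35 − 14 = 21 days early. The Visit 3 window opens on Day 32, so these values precede it by 32 − 23 = 9 to 32 − 14 = 18 days.

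**3. Dependence on the Visit 2 date** (the exit must come after Visit 2):
- Visit 2 on Day 12: exits on Days 14–23, 12 to 21 days early.
- Visit 2 on Day 15: exits on Days 16–23, 12 to 19 days early.
- Visit 2 on Day 18: exits on Days 19–23, 12 to 16 days early.

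**4. Formula against table.** Baseline (*d* = 0) gets *s* = 1, which is in no window, while the table puts baseline at 0. Days 15 and 35 become 16 and 36. For TFBUT one allocation changes. An exit on Day 24 without Visit 2 data gets *s* = 25 and goes to Visit 3, although it is 24 − 15 = 9 days from Day 15 and 35 − 24 = 11 days from Day 35. Dropping the +1 alone would leave *d* = 1 without a window, because the Visit 2 window starts at 2.

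**5. Scale.** The planned 200 subjects reproduce with a noncentral-t calculation (power 80.4%). The standard error of the difference is 2.5 × √(2/100) = 0.354 s. The documents give neither an early-exit rate after Visit 2 nor a TFBUT time course, so what follows rests on assumptions.
- *One-arm shift.* If *k* subjects in one arm are relabelled and each exit value differs by *g* seconds from what the model would imply, that arm's mean moves by about *k*/100 × *g*. With *k* = 1 and *g* = 0.5 this is 0.005 s. With *k* = 10 and *g* = 1 it is 0.10 s. Equal exits with equal gaps cancel.
- *Type I error at the margin.* Suppose 2% to 9.1% of subjects are relabelled (20/220 = 9.1%, the whole non-evaluable allowance) and their early treatment difference is 0.25 to 1.0 s more favourable than the true Day 35 difference. The bias *b* is 0.02 × 0.25 = 0.005 s to 0.091 × 1.0 = 0.091 s. One-sided type I error is 1 − Φ(1.96 − *b*/0.354), which gives 0.026 to 0.044 instead of 0.025.

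**The case against.** The effect is probably small. The top of the range needs ten relabelled subjects in one arm and none in the other, which is half the total allowance of 20 through a single pathway. This stands, and it is why the point is an improvement and not a fatal flaw.

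The effect on the primary test is not established. The PPS depends on the Deviations and Evaluability Plan, which may exclude early exits. This also stands. The documents establish the effect on the FAS superiority tests and on the FAS run of the primary test. The effect on the PPS is conditional.

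The 14-day lower limit depends on how a footnote is read. In the text as extracted, the marker on the early-exit TFBUT cell does not match the position of the 14-day note. That note is the only listed one that fits the cell. If it did not apply, an exit on Day 13 after Visit 2 on Day 12 would be 22 days early, so the mistiming would be larger.

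Deleting the sentence discards observed data, although the FAS is meant to be as complete as possible. Yet a subject with a Visit 2 TFBUT stays in the FAS and still informs Day 35 through the model. The discarded value was never a Day 35 observation.

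The Visit 2 window starting at 2 is consistent with the +1 formula. True, but the baseline at 0 and the scheduled days 15 and 35 are not, so the table mixes two conventions.

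**Conclusion.** The concern holds. With Visit 2 data present, exits 14 to 23 days after Visit 1 are analysed as Day 35, which is 12 to 21 days early and wholly outside the protocol's window. This conflicts with the protocol's reason for the Day 35 visit and with its reliance on likelihood without imputation. Exits on Days 24 to 34 also reach Visit 3, but through the window and not through this sentence.

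The size and direction of bias are unknown. The figures of 0.005 to 0.10 s, and 0.026 to 0.044 for type I error, illustrate scale only and rest on the stated assumptions. The sample size is unaffected. The formula mismatch is real but minor, since it changes one TFBUT allocation.

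**What to change.** 1. Delete the next-visit sentence. An early-exit value whose nearest visit already has data is listed only, and Day 35 stays missing for the MMRM.
2. Define study day as visit date minus baseline date, and set the Visit 2 window to 1–24 so that every post-baseline day has a window. With Visit 2 data, exits on Days 14–24 are then listed only.
3. Add a sensitivity analysis of the TFBUT and discomfort models that removes from the Day 35 cell any early-exit value taken before Day 32. This covers Days 25–31, which still map to Visit 3.
4. Report the number of such values by arm.

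The cost is SAP wording, derivation code, one extra run and slightly fewer Day 35 records. SAP section 11.1 records that, at this version, "The study database is not yet locked and masked treatment code has not been broken". At that stage the affected records could be counted and the rule changed while still masked. The LLT analysis was itself changed then by SAP amendment alone.

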2.4.2 Unscheduled visits

All data collected at unscheduled visits will be listed.

Adverse event (AE) and exposure to study treatment data collected at unscheduled visits will be used.

3 Analysis Sets

The **Screened Set (SCR)** will consist of all subjects who signed the informed consent form (ICF).

The **Randomized Set (RS)** will consist of all subjects who were randomized to one of the study treatment arms.

The **Full Analysis Set (FAS)** is used to describe the analysis set which is as complete as possible and as close as possible to the intent-to-treat (ITT) principle of including all randomized subjects. The FAS will include all randomized subjects who have at least 1 post-baseline primary endpoint (TFBUT) assessment.

The **Per Protocol Set (PPS)** will consist of FAS subjects who satisfy all inclusion/ exclusion criteria and who have no major PDs, which will be specified in the Deviations and Evaluability Plan (DEP).

The **Safety Analysis Set** will include all subjects exposed to post-randomization study product.

Evaluability for all subjects will be determined prior to breaking the code for masked study treatment assignment.

The primary and secondary efficacy analyses will be performed on both the FAS and PPS with the PPS providing the primary inference for the non-inferiority hypothesis and the FAS providing the primary inference for the superiority hypotheses.

Supportive analyses of the primary hypothesis will be conducted using the FAS. Similarly, supportive analyses of the secondary hypotheses will be conducted using the PPS.

The number of subjects excluded from the FAS and PPS and a listing of excluded subjects with reason for exclusion will be presented. Any inconsistencies in key study results between the FAS and PPS will be examined and discussed in the CSR.

All efficacy analyses will be according to randomized assignment (regardless of the study treatment they received).

Safety analyses will be conducted using the Safety Analysis Set on a treatment-emergent basis. The main safety analyses will focus on the investigational products (SYSTANE BALANCE, REFRESH OPTIVE Advanced/ OPTIVE PLUS [UK]). For treatment-emergent safety analyses, subjects will be categorized under the actual study treatment received.

Subjects exposed to an incorrect study treatment for the entire study treatment period will be included in the group corresponding to the study treatment received. Subjects exposed to an incorrect study treatment for a portion of the study treatment period will be accounted for under the actual study treatment the subject was first exposed to in the study.

4 Subject Characteristics and Study Conduct Summaries

Subject characteristics and study conduct summaries include tables and listings such as a subject disposition table, demographics and baseline characteristics tables (including age, sex, race and ethnicity), prior medications table, medical history table, listing of study treatment assignment by investigator and listing of subjects excluded from key analysis sets. Descriptive summary statistics will be presented by study treatment and overall.

No tests for differences in subject characteristics between study treatment groups will be performed.

4.1 Subject disposition

The number and percentage of subjects (based on the number of randomized subjects) who complete the study will be displayed by study treatment and overall. The primary reason for premature study discontinuation and premature study treatment discontinuation will be displayed by study treatment and overall.

The total number of subjects screened and the number of subjects screened but not randomized will be shown. The reasons for screening failure will be summarized.

The number of subjects within each of the analysis sets used in the study will be given. The reasons for exclusion from each set will be listed.

4.2 Background and demographic characteristics

Demographics, baseline characteristics and key efficacy variables at baseline will be summarized for the RS, FAS, PPS and Safety Analysis Set by study treatment and overall. These tables will also be repeated for the RS for the following subgroups: age, sex and region (see Section 5.3.2 for details on the subgroup categories).

The number and percentage of subjects will be presented for the following categorical variables:

- age (years) (<65, ≥65)
- sex (Female, Male, Unknown, Undifferentiated)

- ethnicity (Hispanic or Latino, not Hispanic or Latino, Not Reported, Unknown)
- race (American Indian or Alaska Native, Asian, Black or African American, Native Hawaiian or Other Pacific Islander, White, Other)
- region (Asia, United Kingdom, United States)
- baseline TFBUT (seconds) (<2, 2-4, >4) (for analysis eye only)
- baseline slit-lamp examination parameters (for analysis eye only)
 - Aqueous flare (None, Faint, Moderate, Marked, Intense)
 - Aqueous cells (< 1, 1-5, 6-15, 16-25, 26-50, >50)
 - Lens (Phakic, Pseudophakic, Aphakic)
 - Status of Lens (No Opacity, Any Opacity, Worsening of Opacity, Not Evaluable)
- baseline horizontal length (Grade 0, Grade 1, Grade 2, Grade 3) (for analysis eye only)
- baseline sagittal height (Grade 0, Grade 1, Grade 2, Grade 3) (for analysis eye only)
- [REDACTED]

Descriptive statistics will be presented for the following continuous variables:

- age (years)
- baseline TFBUT (seconds) (for analysis eye only)
- baseline Global Ocular Discomfort VAS score
- [REDACTED]
- [REDACTED]
- baseline BCVA (for analysis eye only)

All demographic and baseline data will be listed by treatment, center, subject and eye (where applicable) for the RS.

